APPENDIX 2: DEFINITION OF AMYLOIDOSIS, MYELOMA AND RELATED DISEASES

Amyloid

- Tissue biopsy showing red-green birefringence in cross polarised light when stained with Congo red by Puchtler's method

Overt Non-Amyloid manifestations of Multiple Myeloma

- Lytic bony lesions (>4 if limited to skull only)
- Hypercalcaemia, hyperviscosity or plasmacytomata

Amyloid-related organ involvement causing organ dysfunction

For details please refer to Gertz et al. Definition of organ involvement and treatment response in immunoglobulin light chain amyloidosis (AL): a consensus opinion from the 10th International Symposium on Amyloid and Amyloidosis. Am J Hematol. 2005 Aug;79(4):319-28.

Defining organ involvement	
Kidney	24-hour urine protein >0.5 g per day, predominantly albumin
Heart	Echo: mean left ventricular wall thickness >12 mm, no other cardiac cause or severe diastolic dysfunction in presence of NT-ProBNP >150 pMol/L and low voltage complexes on ECG without any other cause for these abnormalities
Liver	Total liver span >15 cm in the absence of heart failure or alkaline phosphatase >1.5 times institutional upper limit of normal
Gastrointestinal tract	Symptomatic GI disturbance with or without direct biopsy verification with
Nerve	Peripheral: clinical; symmetric lower extremity sensorimotor peripheral neuropathy Autonomic: gastric-emptying disorder, pseudo-obstruction, voiding dysfunction not related to direct organ infiltration, postural hypotension
Soft tissue	Tongue enlargement, clinical Arthropathy Myopathy by biopsy or pseudohypertrophy Lymph node enlargement

Number of organs involved by amyloid

One to 5 of the following organ systems could be involved by amyloid;

- Renal
- Gastro-intestinal (including liver)
- Cardiac
- Nerves (peripheral and/or autonomic)
- Miscellaneous (e.g. significant soft tissue, factor X deficiency, adrenal insufficiency)

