2.3.2 Secondary endpoints

Clonal response rate (based on paraprotein and FLCs) is defined as the proportion of patients who achieve at least a PR within 3 months, at 3 months, within 6 months and at 6 months after trial registration.

Amyloidotic organ response rate is defined as the proportion of patients who achieve organ response within 3

months and within 6 months of trial registration.

Time to Amyloidotic organ response is defined as the time from the dose allocation to first achieving organ response.

The number of patients experiencing dose delays will be defined as the number of patients experiencing delays in treatment with any of the study treatments.

KTD compliance: Patients will be regarded as compliant to treatment where treatment is received as per protocol until withdrawal from treatment and have no more than 1 dose omission of Carfilzomib, 5 of Thalidomide or 1 of Dexamethasone during each cycle.

Relative Dose intensity will be calculated as the percentage ratio between the received and planned dose intensities, where dose intensity is the cumulative dose divided by the duration of treatment.

3. Analysis Sets

Statistical analysis will be descriptive for all endpoints, and will be summarised overall and by dose cohort. All safety analyses will be based upon the safety analysis set; safety data from patients not included in this analysis set will be listed separately. All efficacy analyses will be based upon the per protocol set. Patients who do meet the criteria to be included in each of analysis sets will have the reasons for emission listed. A sensitivity analysis on the efficacy endpoints may be considered if the total number of patients in each of the analysis sets differs by more than 3 patients.

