3.3 Per protocol set

The per protocol set will include all patients with at least one post baseline efficacy assessment who receive at least one dose of Carfilzomib and have no protocol deviations with relevant impact on efficacy.

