5.1 General calculations

Unless otherwise stated, percentages will be calculated using the total number of patients in the appropriate population as the denominator (i.e. including all patients with missing data for that variable). All analyses will be carried out using SAS unless stated otherwise.

All percentages and means will be rounded to 1 decimal place and standard deviations to 2 decimal places. Values that are below the limit of detection and therefore non-quantifiable will be summarised using the limit of quantification value. For listings, if required, the non-quantifiable value would be reported as an inequality.

Summaries are divided into those participants treated at the recommended dose either during the dose escalation phase (prior to the identification of the recommended dose) or during the dose expansion phase (RD population), and all other participants treated during the dose escalation phase at dose levels other than the recommended dose (Non-RD population). The non-RD population will be split by dose level.

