5.3.2 Secondary endpoints

Safety and toxicity profiles for each cycle and cohort: data will be summarised descriptively, including the proportion of patients experiencing at least one SAE, the number of SAEs experienced per participant, and the number of SAEs experienced according to seriousness criteria, causality, and body system. Toxicity will be summarised according to CTCAE grades and will be summarised as the maximum grade toxicity experienced within each cycle, and overall.

The proportion of patients achieving at least a PR (clonal response) within 3m, at 3m, within 6m and at 6m and the proportion of patients achieving an amyloidotic organ response within 3m and 6m will be presented in tabulated form. Corresponding 90% and 95% confidence intervals will also be presented. Responses at 3 and 6 months will be broken down by response achieved, and by organ (for organ response).

Time to amyloidotic organ response and time to maximum response will be calculated using the Kaplan Meier method. Median time to amyloidotic organ response and median time to maximum response will be presented, with corresponding 95% confidence intervals.

The proportion and number of patients alive at 6 months and patients progression free at 6 months will be presented with corresponding 90% and 95% confidence intervals. If appropriate, Kaplan Meier curves for progression free survival may be explored.

Each patient will be assessed for their maximum clonal response; the number and proportion of participants in each response category within 6 cycles of treatment will be presented with corresponding 95% confidence intervals. Patients who do not achieve a maximum response will be summarised as, "no maximum response".

Feasibility of delivering treatment according to protocol schedule will be summarised descriptively to include the number of patients requiring dose delays and/or reductions, the number of patients withdrawing from treatment, and reasons for dose delays / reductions and withdrawals. Time on treatment and reasons for stopping treatment will also be presented. The number of doses missed will be summarised overall and by cycle.

6. Reporting and Dissemination of the Results

Final analysis will be carried out after the last participant's last data item.

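### By-organ response percentages default to the whole per protocol set, so patients without the organ involved enter the denominator and the result depends on case mix

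*SAP*

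**What the plan says.** SAP 5.1 gives a default rule for percentages, which applies unless another is stated: "percentages will be calculated using the total number of patients in the appropriate population as the denominator". A parenthesis adds that this means "including all patients with missing data for that variable".

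SAP section 3 names the population: "All efficacy analyses will be based upon the per protocol set". SAP 3.3 defines it: "The per protocol set will include all patients with at least one post baseline efficacy assessment who receive at least one dose of Carfilzomib", with no protocol deviation relevant to efficacy. Organ involvement is not part of that definition, and neither SAP section 3 nor Protocol 19.2 defines an organ-involved or organ-evaluable set.

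The endpoint in SAP 2.3.2 is worded per patient: "Amyloidotic organ response rate is defined as the proportion of patients who achieve organ response" within 3 and within 6 months of registration. SAP 5.3.2 then adds a breakdown: "Responses at 3 and 6 months will be broken down by response achieved, and by organ (for organ response"). It gives no denominator for that breakdown. Protocol 18.3 and 19.4 say the same.

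Involvement varies between patients. Protocol Appendix 2 states: "One to 5 of the following organ systems could be involved by amyloid". Protocol 6.3.1 requires amyloid-related organ dysfunction or an organ syndrome at entry, but in no particular organ.

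**The concern.** A by-organ response rate is meant to show how often an affected organ improves. If patients whose organ was never affected sit in the denominator, the figure also reflects how common involvement of that organ was among those recruited. Two dose groups with the same response among affected patients can then show different percentages.

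SAP 1.3 says that the expansion cohort should give an understanding of efficacy for the design of further trials. The organ rates are descriptive, so the reported numbers are themselves the result, and a reader planning a later trial could take a diluted figure for the response rate in affected patients.

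**Working it through.** The plan states no organ response rate and no precision for one, so there is no figure to reproduce. The check has two parts.

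**Which organs are diluted for certain.** Appendix 4 (response) is set beside Appendix 2 (involvement):

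- Kidney: response requires pretreatment urine protein above 0.5 g/day, the threshold that also defines involvement. A patient at or below it cannot respond. The one gap is that Appendix 2 also asks for predominantly albumin.
- Liver: the alkaline phosphatase criterion needs an abnormal starting value, so a patient with a normal value cannot meet it. Involvement needs more than 1.5 times the upper limit, so a mildly raised value lies between the two. The alternative criterion, a decrease in liver size, states no baseline requirement.
- Heart: the criteria are changes in septal thickness, ejection fraction, NT-proBNP or tissue Doppler. None requires cardiac involvement at baseline, so an uninvolved patient could be counted as a non-responder or as a responder.
- Nerve states no baseline requirement. Soft tissue refers to affected tissue, which presupposes involvement.

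**Size.** Let N be the patients in the set, k those with the organ involved and x the responders. Where uninvolved patients cannot respond:

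reported rate = x/N = (k/N) × (x/k), that is, share involved × rate among involved.

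Inputs:

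- N = 6 + 20 = 26: the minimum of 6 patients at the recommended dose (SAP 2.3.1) plus 20 in expansion (SAP 1.4), before per protocol exclusions.
- k and x are assumptions, because the documents give neither organ prevalence nor an expected organ response rate.
- Intervals are exact (Clopper-Pearson) 95%.

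| Involved k | Responders x | As written, x/26 | Among involved, x/k |
|---|---|---|---|
| 10 | 3 | 11.5% (2.4 to 30.2) | 30.0% (6.7 to 65.2) |
| 10 | 4 | 15.4% (4.4 to 34.9) | 40.0% (12.2 to 73.8) |
| 13 | 6 | 23.1% (9.0 to 43.6) | 46.2% (19.2 to 74.9) |
| 20 | 10 | 38.5% (20.2 to 59.4) | 50.0% (27.2 to 72.8) |
| 26 | 13 | 50.0% (29.9 to 70.1) | 50.0% (29.9 to 70.1) |

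The identity for the second row: 10/26 × 4/10 = 38.5% × 40.0% = 15.4%. In that row the interval as written does not contain the 40.0% seen among involved patients, and it is narrower because its n is too large for the organ-specific question.

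Case mix alone moves the result. Hold the rate among involved patients at 40% and change only k: with k = 10 the figure as written is 4/26 = 15.4%; with k = 20 it is 8/26 = 30.8%.

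**The case against.** The strongest reply is that SAP 5.1 is a general default and that its appropriate population could mean, for an organ table, the patients with that organ involved. The SAP does use a group outside section 3 once: baseline characteristics are tabulated for all registered eligible patients (SAP 5.3.1). That is stated explicitly there, however, whereas no such statement exists for organ response and section 3 assigns every efficacy analysis to the per protocol set. If the narrower population is intended, it needs to be written.

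These parts of the opposing case stand:

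- The parenthesis on missing data does not settle the matter. An organ that was never involved is not missing data, and Protocol 12.2 separates not applicable from not done. The point rests on the main clause of the rule.
- Confidence intervals by organ are not clearly promised. The sentence on 90% and 95% intervals in SAP 5.3.2 follows the overall proportions, and the breakdown could be read as counts. The intervals above show what would follow if they were produced.
- The analyses are descriptive with no testing (SAP 5.2), and Protocol 19.1 makes clonal response the primary measure of activity.

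A reader might infer more than the documents support:

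- That every organ rate is biased low. This is not established for the heart, whose criteria an uninvolved patient could meet, and it is false for any organ involved in all patients.
- That a patient with gastrointestinal involvement can never respond. Appendix 4 has no gastrointestinal criterion, but such a patient may have other involved organs that do have one. Only a patient with no such organ is affected.
- That the overall any-organ rate is diluted in the same way. Entry requires organ dysfunction, so it is not.
- That the rates could not be compared with other AL amyloidosis studies. That depends on the denominators those studies used, which the documents do not give.

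**Conclusion.** The concern holds for the by-organ breakdown. Followed as written, the SAP divides each by-organ percentage by all per protocol patients in the group. For kidney and the liver alkaline phosphatase criterion this lowers the rate in proportion to the share without the required baseline abnormality. For heart it mixes in patients whose classification is not informative about amyloid response, in a direction that cannot be predicted.

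The size cannot be calculated from the documents. Under the assumptions above, with N = 26, the gap runs from 24.6 percentage points (40.0% − 15.4%, 10 involved and 4 responding) through 11.5 points (50.0% − 38.5%, 20 involved and 10 responding) to zero when all are involved. The defined endpoint, overall organ response, is essentially untouched. This is a change that should be made to a descriptive secondary summary; it does not threaten the trial's main conclusions.

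**What to change.** Add to SAP 5.3.2, before the final analysis:

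- Each by-organ response uses as denominator the per protocol patients with that organ involved at baseline under Appendix 2 and assessable under Appendix 4. Assessable should mean that the organ has a response criterion and the baseline value it needs is available. Patients with missing follow-up stay in the denominator, consistent with SAP 5.1.
- For each organ, report the number involved out of N next to the number responding.
- Keep the overall any-organ response rate on the full per protocol set, and report how many patients have as their only involved organ one without an Appendix 4 criterion.

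The cost is a few lines of text and one derived baseline variable per organ. The baseline Amyloid Evaluation already examines organ dysfunction (Protocol 6.1), and its results are recorded as trial data (Protocol 11.1.1). The downside is smaller denominators and wider intervals for each organ. With 10 involved and 4 responding, the exact 95% interval is 12.2 to 73.8% instead of 4.4 to 34.9%. That width reflects the information the trial has on that organ.

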8.1.3 Dose Escalation

Dose escalation will begin at DL0 and will proceed until MTD or the highest planned dose level has been reached. Toxicity data for each cohort will be reviewed by the Safety Review Committee prior to dose escalation, according to the following schema (Table 2).

Table 2. Scheme for dose escalation decision

Identifying MTD	
Number of patients with a DLT following 1 cycle at a given dose level	Escalation decision rule
0 out of 3	Enter 3 patients at the next highest dose level. If current dose level is the highest dose level, this is the MTD; proceed to identifying RD
≥2 out of 3	Dose escalation stopped and next lowest dose identified as MTD. Proceed to identifying RD. If current dose level is lowest dose, no MTD identified.
1 out of 3	Enter 3 more patients at the current dose level. 
 • If 0 out of these additional 3 experience DLT (i.e. total DLTs 1/6), proceed to the next highest dose level. If current dose level is the highest dose level, this is the MTD & current dose level is identified as RD • If 1 or more of these additional 3 experience DLT (i.e. total DLTs >1/6), dose escalation stopped

	and next lowest dose identified as MTD. Proceed to identifying RD

Identifying RD
 
Once the MTD is identified, at least 6 patients must have completed cycle 1 at the RD before enrolment to the dose expansion phase can commence.
 
The RD is defined as the highest dose level at which at most 1/6 patients experience a DLT. If only 3 patients have been treated at the next lowest dose an additional 3 patients are recruited to this dose level. If >1/6 DLTs are then experienced at this dose level, dose level de-escalation continues until the RD is identified.
 
If the MTD is identified as the highest dose level with 0/3 DLTS then an additional 3 patients are recruited to this highest dose level. If >1/6 DLTs are then experienced at this dose level, dose level de-escalation continues until the RD is identified. If ≤1/6 DLTs are experienced then the highest dose level is identified as the RD.
 
If no MTD is identified, no RD is identified and the study will not continue to the dose expansion phase.
	

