19.2 General Considerations

Statistical analysis of clinical endpoint data is the responsibility of the CTRU Statistician. A full statistical analysis plan will be written before any analyses are undertaken. The analysis plan will be written in accordance with current CTRU standard operating procedures and will be finalised and agreed by the following people: the trial statistician and supervising statistician, the Chief Investigator, the CTRU Delivery and Scientific Leads and the Senior Trial Manager. Any changes to the finalised analysis plan, and reasons for changes, will be documented.

All patients that receive at least one dose of Carfilzomib and with no protocol deviations with relevant impact on safety will be included in the safety analysis set.

The per protocol set will include all patients with at least one post baseline efficacy assessment who receive at least one dose of Carfilzomib and have no protocol deviations with relevant impact on efficacy.

Determination of the MTD in the dose escalation phase of the trial will be based on those patients who have received at least one cycle KTD and will be evaluated between the time of receiving the first dose of Carfilzomib in cycle 1 and the first dose of treatment in cycle 2. The safety review committee will review each DLT and attribute the DLT to the loading dose or the registered dose; any DLT attributed to the loading dose will be excluded when determining the MTD.

KTD Patients who do not receive one complete cycle due to experiencing a DLT will be included in the analysis; patients who do not receive at least one complete cycle for reasons other than toxicity, without experiencing a DLT, and who miss a dose of Carfilzomib, more than 14 doses Thalidomide or 2 doses of Dexamethasone in the first cycle, will be replaced. Evaluability will be considered by the safety review committee on an individual basis to account for attributing DLTs and missed doses to the loading or the registered dose.

The RD cohort will include all patients who are registered to receive and receive at least one dose of Carfilzomib at the RD. This cohort will include patients from the dose escalation and dose expansion phases of the study. All patients who do not fulfil these criteria will be included in the non-RD cohort.

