1.4 Sample size and expected accrual

In the dose escalation phase of this study, a minimum of 6 (3 at dose level 0 and 3 at dose level -1) and a maximum of 18 (6 at dose level 0 1 and 2) patients will recruited in a 3+3 design with cohorts of between 3 and 6 patients, in order to determine maximum tolerated dose and recommended dose.

At the recommended dose level identified, a further 20 patients will be recruited to further assess safety and toxicities at the RD.

The study will run in 15 UK centres. The study duration is expected to be approximately 42 months – including 6 months of set up, 24 months of recruitment, 6 months of follow-up and 6 months of analysis/write-up.

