3.5 Dose Cohorts

The RD cohort will include all patients who are registered to receive and receive at least one dose of Carfilzomib at the RD. This cohort will include patients from the dose escalation and dose expansion phases

of the study. All patients who do not fulfil these criteria will be included in the non-RD cohort.

4. Data Handling

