5.3.2 Primary endpoints

The number of patients experiencing DLTs within the first cycle of KTD will be presented, with descriptive summaries of the specific DLTs observed. Summaries will be presented for each dose level. This data will be presented for patients registered to the dose escalation phase of the study only.

Further summaries of longer-term tolerability will also be presented for patients registered to the dose escalation phase to include the maximum toxicity grade experienced within the first three cycles of treatment, overall and by cycle. Individual listings of the toxicities, grade and cycle of all toxicities experienced within the first three cycles will be presented.

The number of patients experiencing any grade 3 or 4 CTCAE toxicity within all cycles of treatment will be summarised. This will be presented overall and by dose cohort, across all cycles as well as by each cycle.

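### The grade 3 or 4 toxicity rate at the recommended dose is planned only for a cohort that includes the patients whose low DLT count selected that dose; it is biased modestly low, and an expansion-only column should be added.

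*SAP*

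**What the plan says.** SAP 5.1 forms a single group from everyone who was given the RD, "either during the dose escalation phase (prior to the identification of the recommended dose) or during the dose expansion phase (RD population". SAP 3.5 says of the RD cohort, "This cohort will include patients from the dose escalation and dose expansion phases", and Protocol 19.2 agrees.

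The rule that picks the dose is in Table 2 of Protocol 8.1.3: "The RD is defined as the highest dose level at which at most 1/6 patients experience a DLT". The same table requires that "at least 6 patients must have completed cycle 1 at the RD before enrolment to the dose expansion phase can commence". SAP 1.4 then plans that "a further 20 patients will be recruited to further assess safety and toxicities at the RD"; Protocol 3.0 and SAP 1.2 give 20 as a maximum.

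The second primary endpoint (SAP 2.1) is the proportion of patients with any grade 3 or 4 toxicity over all treatment cycles. On its reporting, SAP 5.3.2 (Primary endpoints) says: "This will be presented overall and by dose cohort, across all cycles as well as by each cycle". SAP 5.1 splits the non-RD population by dose level but does not split the RD population by phase. DLT counts are shown for escalation-phase patients only, and all analysis is descriptive (SAP 5.2).

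**The concern.** The 6 escalation patients at the RD are there because few of them had a DLT. Had 2 or more had one, the dose would not be the RD. Their early toxicity is thus expected to look better than the true rate at that dose, by construction. The expansion patients enter after the choice and carry no such selection.

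The primary aim of the expansion phase is a further assessment of safety at the RD (Protocol 3.1, SAP 1.3), yet no toxicity result is planned for that phase alone. A reader would see the DLT rate only in patients constrained to at most 1 in 6, and grade 3 or 4 toxicity at the RD only after mixing with them. The error runs in the reassuring direction, on a primary safety endpoint that is meant to inform the design of later trials.

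**Working it through.** **Reproducing the plan's own figure.** The documents state no toxicity rate or precision for the RD cohort; the one figure to reproduce is the escalation size. Enumerating every path through Table 2 gives a minimum of 6 and, over dose levels 0, 1 and 2, a maximum of 6 + 6 + 6 = 18. This matches SAP 1.4: "a maximum of 18 (6 at dose level 0 1 and 2) patients will recruited in a 3+3 design". (Paths that de-escalate to level -1 can reach 24, which does not affect this point.)

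**Inputs.**
- Escalation patients at the RD: 6 evaluable (Protocol 8.1.3, Table 2).
- Expansion patients: 20 (SAP 1.4).
- True cycle 1 DLT rate at the RD, p: not given for this regimen; assumed 10, 20 and 30%.
- True rate of any grade 3 or 4 toxicity over all cycles, g: not given; assumed 40 to 80%. For scale, the earlier single-agent study in AL amyloidosis (Protocol 2.1.3.4) had 7 patients with a grade 3 or higher event and 11 evaluable, so 7/11 = 63.6%.

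**Step 1: DLT rate in the selected six.** Results at other doses are independent of those at the RD, so the DLT count X in the six is Binomial(6, p) restricted to X ≤ 1. Hence

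E[X/6 | X ≤ 1] = p(1-p)^5 / [(1-p)^6 + 6p(1-p)^5] = p/(1+5p).

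This is 6.7%, 10.0% and 12.0% for p = 10, 20 and 30%.

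**Step 2: what pooling would do to a DLT-type rate.** Pooled mean = [6·p/(1+5p) + 20p]/26.
- p = 10%: (0.40 + 2.00)/26 = 9.2%, bias -0.8 points
- p = 20%: (0.60 + 4.00)/26 = 17.7%, bias -2.3 points
- p = 30%: (0.72 + 6.00)/26 = 25.8%, bias -4.2 points

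Simulating the whole escalation rule (100,000 trials for each of two assumed dose-DLT curves: 8, 15, 25, 40% and 5, 10, 20, 30% at levels -1 to 2) agreed with the formula to within 0.1 point. The average bias was -2.4 and -2.2 points pooled, and at most 0.06 points in the expansion patients alone.

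**Step 3: the endpoint that is actually pooled.** Assume every patient with a DLT also counts as grade 3 or 4, and that the other patients have such an event with probability h = (g-p)/(1-p). Then

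bias = (6/26) · [p/(1+5p) - p] · (1-g)/(1-p).

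At p = 20% and g = 63.6%: (6/26) × (-0.10) × (0.364/0.80) = -0.0105, that is -1.05 or about -1.1 points (63.6% would be reported as 62.5% on average).

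| g | p = 10% | p = 20% | p = 30% |
|---|---|---|---|
| 40% | -0.5 | -1.7 | -3.6 |
| 63.6% | -0.3 | -1.1 | -2.2 |
| 80% | -0.2 | -0.6 | -1.2 |

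(Bias in percentage points.)

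**Step 4: the cycle 1 row.** Replace g by the cycle 1 grade 3 or 4 rate, which cannot exceed g. The factor (1-g)/(1-p) rises, so the bias in this row is at least as large as over all cycles. It reaches the Step 2 values only if every cycle 1 grade 3 or 4 event were a DLT.

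**Step 5: bias against precision.** Root mean squared error at p = 20%, g = 63.6%: 9.5 points pooled, 10.8 points expansion-only. Pooling was lower at every combination of p and g in the table. Exact 95% intervals near 65%: 44.3 to 82.8% for 17/26 (half-width about 19 points) and 40.8 to 84.6% for 13/20.

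**The case against.** Four arguments can be made for leaving the plan alone.

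- **The effect is small.** This stands. A reader might take the -2.3 to -4.2 points of Step 2 (p = 20 to 30%) as the size of the problem. The documents do not support that: no table pools a DLT rate, because SAP 5.3.2 shows DLTs for escalation patients only. Many grade 3 or 4 events never entered the selection. A DLT must be treatment-related and fall in the cycle 1 window, most non-haematological events must also fail to resolve within 7 days, grade 3 haematological toxicity is not listed, and DLTs attributed to the loading dose are set aside.
- **Pooling is the more accurate estimator.** This also stands. A reader might infer that the expansion-only figure should replace the pooled one as the main estimate. On these numbers, dropping 6 of 26 patients costs more in variance than it removes in bias. Even for a DLT-type rate at p = 20%, the root mean squared error is 7.5 points pooled against 8.9 expansion-only.
- **Separation is partly planned.** SAP 5.3.2 also gives, for escalation-phase patients, the maximum toxicity grade over the first three cycles, overall and by cycle, with individual listings. Expansion counts could partly be recovered by subtraction. That route covers only three of up to six cycles, and the reader would have to pick the RD patients out of the listings. It does not replace a planned result.
- **The pooling is prespecified and the study is descriptive.** True, and further assessment is compatible with accumulating evidence at one dose. But descriptive figures are what later trials will use, and neither document says that part of the cohort was selected on a related outcome.

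**Conclusion.** The point holds as a modest, systematic downward bias in a primary safety summary, together with the lack of any toxicity result for the expansion phase alone. The direction follows from the selection rule. The size, -0.2 to -3.6 points over all cycles, rests on assumed rates, on 6 and 20 patients, and on every DLT also counting as grade 3 or 4. Partial overlap between the two would shrink it; fewer than 20 expansion patients would enlarge it, since the weight of the selected patients is 6/(6 + number in expansion). It does not invalidate the choice of dose or the pooled estimate. It warrants an added figure and a label.

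**What to change.** In SAP 5.1 and 5.3.2 (Primary endpoints):

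- Keep the RD cohort as defined, with patients from both phases.
- Add beside it the proportion with any grade 3 or 4 toxicity among expansion-phase patients alone, across all cycles and by cycle, with an exact confidence interval.
- Label the pooled figure as including the escalation patients whose count of at most 1/6 DLTs selected the dose.

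The cost is one extra table column and a footnote. Conduct, sample size and data collection do not change. The added column has the wider interval shown in Step 5, and the more precise pooled figure remains next to it.
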